5.3. Long Term Follow up

Subjects who completed therapy, including treatment with or without retreatment, treatment with maintenance, or discontinued treatment for any reason other than clinical or radiological progression will enter the Long Term Follow up period. Subjects will be evaluated every 8 weeks for one year (until Amendment 5), and every 9 weeks (Amendment 6). During this Long Term Follow up Period, if a subject progresses or receives an intervening anti-cancer therapy, the subject will then enter the Survival Follow up Period.

Subjects who discontinue treatment due to clinical or radiological progression or Withdraw Consent from study treatment(s) will not enter Long Term Follow up, but will enter survival follow up as outlined below.

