8.12. Permanent Discontinuation of Study Drug Due to Adverse Events

INT230-6 should be permanently discontinued for a subject due to the occurrence of any of the following AEs that have not resolved prior to the next treatment

- Any CTC Grade ≥ 3 immunologic related event that persists >1 week despite treatment per institutional guidelines
- CTC Grade 4 neutropenia > 7 days or neutropenic fever
- Persistent \geq CTC Grade 3 anemia despite growth factor support
- Platelets $< 70,000$ for superficial tumors, $< 100,000$ for deep tumors
- \geq CTC Grade 3 elevation in liver enzymes
- \geq CTC Grade 4 neuropathy
- Creatinine > 1.5 mg/dl
- Any anaphylactic type reactions
- \geq Grade 3 nausea or vomiting that persists despite maximal supportive care

- Any AE, laboratory abnormality, or intercurrent illness which, in the judgement of the Investigator, presents a substantial clinical risk to the subject with continued treatment

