12.1.4. Follow-up Period

Follow-up visits will be conducted after completion of the Treatment Period (induction and maintenance for those cohorts with maintenance treatment) or as indicated in Section 5.4. Patients who receive all 5 treatment doses or discontinue treatment for any reason except Disease Progression, or Withdrawal of consent should enter Long Term Follow up Period. These patients are to be evaluated every 9 weeks including scans until disease progression or they receive an intervening anti-cancer medication. After documented disease progression or receipt of an intervening anti-cancer medication, patients will enter Survival Follow up. During this time, patients will be contacted every 3 months for patient status (phone call or clinic visit). For subjects who discontinue treatment due to progression, follow-up should be completed approximately every 3 months as noted below (survival follow up). Completion of subsequent follow-up visits will depend on the status of the subject at the end of treatment. All subjects will be followed from the last visit until progression, initiation of a new therapy, or the duration of the study (4 years), whichever occurs first.

Following completion of the treatment and follow-up periods, all subjects will be followed for survival after completion of treatment phases and through the follow up period of the protocol. Subjects will have their survival status assessed approximately every 3 months by either a telephone, in-person contact, or chart review until study completion or termination by the Sponsor. No other data (e.g., subsequent therapies, performance status etc.) beyond survival will be collected during these calls/visits.

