7. Whether event was serious
8. Whether event is ongoing (i.e., not resolved).

Relationship to Study Drug

The relationship of each adverse event to study drug will be defined as “not related” or “related”. The Investigator is responsible for determining the study drug relationship for each adverse event that occurs during the study. Assessments are to be recorded on the appropriate CRF page.

Not related

The temporal relationship of the clinical event to study drug administration makes a causal relationship unlikely, or other drugs, therapeutic interventions or underlying conditions provide a sufficient explanation for the observed event.

Related

The temporal relationship of the clinical event to study drug administration makes a causal relationship possible, and other drugs, therapeutic interventions or underlying conditions do not provide a sufficient explanation for the observed event.

Action(s) Taken

The actions taken with study drug in response to an adverse event are described. One or more of these are to be selected:

- No action taken
- Study drug permanently discontinued due to this adverse event
- Study drug temporarily interrupted
- Study drug dosage adjusted

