Adverse events will be coded using the Medical Dictionary for Regulatory Activities (MedDRA) to categorize a system organ class and a preferred term for each adverse event. The number of subjects who experienced at least 1 adverse event, study drug related adverse event, severe (Grade 3 or above) adverse event, serious adverse event, and the number of subjects withdrawn due to adverse events will be summarized. For each system organ class and preferred term, summaries will be made with respect to the number and proportion of subjects having at least 1 occurrence of an adverse event during the study, using the worst grade reported within a subject. The incidence of adverse events will be presented overall, by system organ class and preferred term, intensity (based on NCI CTCAE Version 4.03), and additional grouping by severity and relationship to study drug. Individual listings of adverse events will be provided.

DLTs and study drug-related Grade >2 adverse events will be listed individually.

Physical Examination

Abnormal PE findings with onset prior to first dose of study drug will be recorded as medical history. Any abnormal or clinically significant findings on or after dosing will be recorded as an adverse event. Clinical significance will be determined by the Principal Investigator at each site.

Individual medical/surgical history will be listed by subject. Individual abnormal or clinically significant PE findings after dosing will be recorded as an adverse event and listed separately with AEs.

Vital Signs

Vital sign measurements and change from baseline will be summarized. Vital signs include weight, systolic blood pressure (SBP), diastolic blood pressure (DBP), body mass index (BMI, derived), heart rate, oxygen saturation, and temperature. Individual vital sign measurements will be listed.

ECGs

ECG data will be read and interpreted locally. Summary statistics of ECG overall interpretation will be displayed. Per subject ECG test results at will be listed.

Abnormal clinically significant ECG findings on or after informed consent will be recorded as an adverse event and displayed with AEs.

Clinical Laboratory Tests

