4.1.4. Long Term Follow up

Subjects who complete a full course of treatment including those who receive retreatment or who have discontinued treatment for any reason other than clinical or radiological progression will enter the Long Term Follow up period. During this time, subjects will be evaluated every 8 weeks for the first year and every 3 months thereafter. During this Long Term Follow up Period, if a subject progresses or receives an intervening anti-cancer therapy, the subject will then enter the Survival Follow up Period.

Subjects who discontinue treatment due to clinical or radiological progression or are Lost to Follow up or Withdraw Consent will not enter Long Term Follow up, but will enter survival follow up as outlined below.

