- number and percentage of subjects with one or more severe (Grade 3 or above) TEAEs

- number and percentage of subjects with one or more severe (Grade 3 or above) INT230-6 monotherapy treatment-related TEAEs (all monotherapy cohorts combined)
- number and percentage of subjects with one or more severe (Grade 3 or above) related TEAEs for DEC and DEC2 cohorts (not by individual drug agent)
- number and percentage of subjects with one or more severe (Grade 3 or above) related TEAEs for FEC cohort (not by individual drug agent)
- number and percentage of subjects with one or more serious adverse events (SAEs)
- number and percentage of subjects with one or more INT230-6 monotherapy-related SAEs (all monotherapy cohorts combined)
- number and percentage of subjects with one or more related SAEs for DEC and DEC2 cohorts
- number and percentage of subjects with one or more related SAEs (for FEC cohort)
- number of deaths (if any)
- number and percentage of subjects with one or more TEAEs resulting in discontinuation from the study

The frequency and percentage of TEAEs by SOC and PT for each treatment will be tabulated. The frequency and percentage of TEAEs by SOC/PT by maximum severity (Grade 1 - 5) will be presented by treatment. The frequency and percentage of Related TEAEs and of All TEAEs (related or unrelated) by PT and by maximum severity will be presented for the following cohorts:

- Overall Monotherapy
- Monotherapy Cohorts A1/B1/EA/EC
- Monotherapy Cohorts EC2/EC3
- Combination Pembrolizumab Cohorts DEC/DEC2
- Combination Ipilimumab Cohort FEC
- Monotherapy Sarcoma Subjects
- Combination Ipilimumab Cohort FEC Sarcoma Subjects
- Note:Sarcoma includes chordoma.

The number and percentage of TEAEs by SOC/PT considered related to study drug will be summarized. Number and percentage of subjects experiencing Grade 3 or higher TEAEs by SOC/PT will be summarized. Number and percentage of subjects experiencing Serious TEAEs by SOC/PT will be summarized. The frequency and percentage of TEAEs that lead to study discontinuation will be presented. If a subject moves from monotherapy to combination therapy treatment, the summary adverse events will be calculated based on the treatment at the time of the event.

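### SAP 10.1 counts adverse events that lead to leaving the study, so read literally it can understate adverse-event-driven stopping of INT230-6

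*SAP*

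**What the plan says.** SAP 10.1 defines both of its AE discontinuation summaries on the study rather than on treatment. The overall summary gives the "number and percentage of subjects with one or more TEAEs resulting in discontinuation from the study". Later in the same section: "The frequency and percentage of TEAEs that lead to study discontinuation will be presented". The protocol's safety analysis text (14.3.5) is less specific: "the number of subjects withdrawn due to adverse events will be summarized", without saying withdrawn from what.

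Stopping INT230-6 for an AE is a distinct event in the protocol. Section 8.12 states that "INT230-6 should be permanently discontinued for a subject due to the occurrence of any of the following AEs" it goes on to list. Section 13.1 provides an action-taken category for it: "Study drug permanently discontinued due to this adverse event".

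Stopping drug is not the same as leaving. Protocol 5.3 says that subjects who "discontinued treatment for any reason other than clinical or radiological progression will enter the Long Term Follow up period". Protocol 12.1.4 says that those who "discontinue treatment for any reason except Disease Progression, or Withdrawal of consent should enter Long Term Follow up Period". SAP 4.1.4 repeats the rule for subjects who "have discontinued treatment for any reason other than clinical or radiological progression will enter the Long Term Follow up period".

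**The concern.** The two events differ by design. An AE-driven stop of INT230-6 normally moves the subject from treatment to follow-up, with the subject still on study. A summary that counts only AEs leading to study exit would not count that subject.

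Safety and tolerability is the primary objective, and a reader of the study report will look for the proportion of subjects who stopped the investigational drug because of an AE, and for which events caused it. The Grade 3 or higher rate does not answer this. Some triggers in Protocol 8.12 carry no toxicity grade: the platelet thresholds, the creatinine threshold, and any AE or laboratory abnormality that the investigator judges a substantial risk. A programmer who follows SAP 10.1 as written would produce a discontinuation row that could be mistaken for the drug-stopping rate and fall below it.

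**Working it through.** The documents state no discontinuation rate, so there is no figure to reproduce. The check compares definitions and then illustrates the scale.

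**Step 1. What each planned output counts.**

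| Output | Event counted | Event terms (SOC/PT)? |
|---|---|---|
| SAP 10.1 overall-summary row | AE leading to study discontinuation | No |
| SAP 10.1 frequency of TEAEs leading to discontinuation | AE leading to study discontinuation | Layout not stated |
| SAP 8.1 disposition table | Early discontinuation by reason, apart from reason for end of study | No |
| SAP 8.4, INT230-6 | Partial or incomplete dosing, reasons for interruption | No |
| SAP 8.4, pembrolizumab and ipilimumab | Permanent discontinuation with reasons | No |
| SAP 10.1 AE listing | Action Taken and a separate discontinued yes/no field | Yes, but a listing only |

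No table uses the Action Taken field. None summarises, by SOC and PT, the AEs that led to stopping INT230-6.

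**Step 2. Does the SAP separate the two events?** Yes. The disposition listing in SAP 8.1 carries the reason for stopping study drug early and the reason for study discontinuation as separate items. A literal reading of the SAP 10.1 wording is therefore a reasonable one.

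**Step 3. Size of the possible shortfall.** Let D be the number of subjects who stop drug for an AE and f the share of them who also leave the study because of it. The literal row then shows D × f, and the shortfall is D × (1 − f), from zero (f = 1) to D (f = 0). The row could include a subject outside D only if that subject left the study for an AE that was not recorded as stopping drug.

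**Step 4. Illustration.** The denominator is the final enrollment of 110 from SAP 5, standing in for the All Treated Population. D and f are assumptions; neither is in the documents. Row counts are D × f rounded to whole subjects (halves to the even number), and percentages are count ÷ 110.

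| D (assumed) | f = 0 | f = 0.25 | f = 0.5 | f = 1 |
|---|---|---|---|---|
| 3 (2.7%) | 0 (0%) | 1 (0.9%) | 2 (1.8%) | 3 (2.7%) |
| 6 (5.5%) | 0 (0%) | 2 (1.8%) | 3 (2.7%) | 6 (5.5%) |
| 11 (10.0%) | 0 (0%) | 3 (2.7%) | 6 (5.5%) | 11 (10.0%) |
| 17 (15.5%) | 0 (0%) | 4 (3.6%) | 8 (7.3%) | 17 (15.5%) |

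Exact Clopper-Pearson 95% limits are the beta quantiles B(0.025; x, n − x + 1) and B(0.975; x + 1, n − x). For x = 11, n = 110 they are 5.1% to 17.2%. For x = 0 the upper limit is 1 − 0.025^(1/110) = 3.3%, so the interval is 0% to 3.3%. If D = 11 and no one left the study, the interval around the reported row would exclude the true 10.0%. If all left, there would be no discrepancy.

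**The case against.** The strongest reply has four parts.

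**The primary measure is untouched.** Protocol 4.2 and SAP 10 assess safety and tolerability by the rate of attributed Grade 3 or higher AEs, and the discontinuation row does not feed it. This stands. A reader might infer that the trial's tolerability rate is understated; the documents do not support that.

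**The information is planned elsewhere.** SAP 8.1 tabulates reasons for early discontinuation among treated subjects, and adverse event is one of the reason categories in Protocol 12.1.5. The AE listing in SAP 10.1 carries Action Taken with SOC and PT, and AEs that led to discontinuation are listed separately. This stands in part: nothing is lost from the database, and an aggregate count should appear in disposition. SAP 8.1 does not say whether one reason is taken per subject, but Protocol 12.1.5 documents primary reasons, with progression and AE as alternatives. A subject with both could be coded to progression. Disposition gives no event terms, grade or relatedness, and the separate listing does not say what was discontinued.

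**SAP 8.4 loses nothing,** because disposition covers INT230-6. This is fair as far as counts by reason go, with the same limits.

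**The word *study* may be loose.** Protocol 8.11 says a subject with an over-long delay should come off study, while 12.1.6 lists the same delay as a reason to stop investigational product with follow-up continuing. Protocol 12.1.5 has subjects who discontinue from the study still completing follow-up visits. The row may have been meant as treatment discontinuation, and the table shells that might settle it are in a companion document outside the protocol and SAP. This also stands, so understatement is a risk and not an established fact. The wording needs correcting on either reading.

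**Conclusion.** The point holds as a gap in the AE summaries. As written, both SAP 10.1 discontinuation outputs can understate AE-driven stopping of INT230-6, by anything from none to all of the true count, and no planned SOC/PT summary shows which AEs caused it. This rests on a literal reading of *study* and on an unreported share of drug-stoppers who also leave the study.

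A reader might go further and expect the row to be near zero whatever the true rate. That requires both the literal reading and a very small share leaving; the documents establish neither. This is an inexpensive improvement to safety reporting. It shows no bias in the trial's primary safety rate.

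**What to change.** In SAP 10.1:

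- Define *treatment discontinuation* and *study discontinuation*, and use the terms consistently, including in the separate listing of AEs that led to discontinuation.
- Add an overall-summary row and an SOC/PT table for TEAEs whose Action Taken is "Study drug permanently discontinued due to this adverse event", by treatment group.
- In the combination cohorts, split by agent if the eCRF records Action Taken by agent. The documents do not show that it does.
- Keep study discontinuation as its own row.

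The field is already collected and planned for the AE listing, so the cost is one extra derivation and one table. The reported discontinuation rate may be less favourable than the current row would show.

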10.2. Clinical Laboratory Evaluations

Clinical laboratory values will be summarized in SI units. Severity grades will be programmatically calculated using standard American Medical Association's (AMA) laboratory normal ranges [AMA Manual of Style, AMA 2009] and the quantitative NCI CTCAE 4.03 criteria (when available for a specific laboratory abnormality). Laboratory values considered to be normal by CTCAE criteria, meaning they do not qualify as Grade 1 - 4, will be assigned a severity grade of 0. For laboratory tests without any CTCAE criteria, toxicity grades will be recorded as 99.

Summary statistics of numerical laboratory test results and changes of test results from baseline will be reported by treatment for hematology, coagulation, serum chemistry, and urinalysis at each scheduled time point. For values with categorical results, the frequency and percentage of each result category will be tabulated at each scheduled time point by treatment. Shift tables will also be included reporting change from baseline category (low, normal, high) to post-dose category (low, normal, high) for cohorts and overall. Abnormal laboratory values that lead to a change in subject management or that are considered to be of clinical significance will be reported as an adverse event (serious adverse event if relevant) and summarized by SOC/PT and according to severity in the appropriate AE tables. Clinical significance will be determined by the Principal Investigator at each site.

Individual test result records, including repeat assessments, and comments for hematology, coagulation, serum chemistry, and urinalysis will be displayed in listings. Laboratory values outside normal limits will be identified with flags for high, low, and normal limits in the listings. Pregnancy test results will be displayed in a listing.

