10. Prior systemic radiation therapy (either IV, intrahepatic or oral) completed at least 4 weeks prior to study drug administration; **(for ipilimumab combination please see supplement FEC exclusion criteria).**
11. Prior focal radiotherapy completed at least 2 weeks prior to study drug administration.
12. Prior major treatment-related surgery completed at least 4 weeks prior to study drug administration.
13. No prior primary or metastatic brain or meningeal tumors unless clinically and radiographically stable as well as off steroid therapy for at least 2 months.
14. Life expectancy ≥ 8 weeks; **(for ipilimumab combination please see supplement FEC inclusion criteria).**
15. A female participant is eligible to participate if she is not pregnant, not breastfeeding, and at least one of the following conditions applies:
 - a. Not a woman of childbearing potential (WOCBP)
 - b. A WOCBP subject who may become pregnant or who are sexually active with a partner and who could become pregnant agrees to use an effective form of barrier contraception during the study and for at least 180 days in monotherapy; **(for pembrolizumab and ipilimumab combinations please see supplements DEC/DEC2 and FEC for pregnancy criteria).** (Male subjects must agree to use contraception and refrain from sperm donation during the study for 180 days after administration of study drug.)
16. Have adequate organ function as defined by the below screening laboratory values that must meet the following criteria:
 - a. WBC $\geq 2000/\mu\text{L}$ ($\geq 2 \times 10^9/\text{L}$).
 - b. Neutrophils $\geq 1000/\mu\text{L}$ ($\geq 1 \times 10^9/\text{L}$); **(for pembrolizumab and ipilimumab combinations please see supplements DEC/DEC2 and FEC for neutrophil criteria).**
 - c. **For subjects with planned superficial only injections:** PT, PTT/aPTT, and INR $\leq 1.5 \times \text{ULN}$, Platelets $\geq 70 \times 10^3/\mu\text{L}$ ($\geq 70 \times 10^9/\text{L}$), Hemoglobin $\geq 8 \text{ g/dL}$
 - d. Creatinine within the institution's laboratory upper limit of normal or calculated creatinine clearance $> 50 \text{ ml/min}$; **(for pembrolizumab combination please see supplements DEC/DEC2 for creatine criteria).**
 - e. ALT (SGOT)/AST (SGPT) $\leq 2.5 \times \text{ULN}$ without, and $\leq 5 \times \text{ULN}$ with hepatic metastases.

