- Vital sign measurements to include temperature, pulse, O₂ saturation and resting blood pressure as defined in the Time and Events Schedule ([Table 11](#) for every 28 day dosing and [Table 12](#) for every 14 day dosing). Vital signs will be obtained before injection and then 15, 30, 60 post injection. In addition, 180 and 360 minutes post injection vital signs are collected at C1D0.
- Weight;
- Assessment of signs and symptoms;
- Adverse Event Assessment;
- ECG;
- ECOG performance status;
- Serum sample for pharmacokinetics is eliminated in Amendment 6. Clinical laboratory tests (local laboratories; Hematology (using ~5 mL of blood), coagulation

and clinical chemistry laboratories (using ~5 mL of blood) **must be performed and reviewed before dosing**. Labs do not need to be repeated if obtained within 72 hours of starting treatment). This includes a CBC with differential and Chemistry as outlined in Section 12.1.2;

- Any new \geq Grade 3 laboratory abnormality such as liver function test elevations, electrolyte fluctuation, or hematologic deterioration should be assessed for potential risk to continued dosing. In the event of uncertainty, the Sponsor Medical Monitor should be contacted;
- Urinalysis;
- Serum or urine pregnancy test to be performed locally (for all women of childbearing potential; pregnancy test must be negative before study drug administration to continue);
- CT/MRI Brain screening: CT/MRI Brain, only if clinically indicated by the development of new symptoms that suggest new CNS involvement;
- Tumor imaging (CT/MRI or PET/CT chest/abdomen/pelvis) **to be conducted only if imaging has not occurred within previous 29 days**;
- US/CT measurements of injected tumor;
- Response assessment and documentation;
- Cryopreserved peripheral blood mononuclear cells (PBMCs) and serum. **Collection eliminated in Amendment 6.**
- Tumor and blood samples that are available after completion of designated analyses may be used in the future for identification of potential predictive and/or pharmacodynamic markers. These assessments will provide exploratory insights into the immunomodulatory activity of INT230-6.;
- Concomitant medications;
- INT230-6 injections (after all other evaluations for the visit according to the Time and Events ([Table 12](#)) have been completed except for the post injection vital signs);

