13.1. Definitions

An adverse event is any undesirable sign, symptom, clinically significant laboratory abnormality, or medical condition occurring after starting study treatment, even if the event is not considered to be study drug-related. Each adverse event is to be reported on an Adverse Event CRF page. Adverse events are graded using the Cancer Therapy Evaluation Program (CTEP) CTCAE, Version 4.03. If CTCAE grading does not exist for an adverse event, the severity of mild (1), moderate (2), severe (3), life-threatening (4), and death related to an adverse event (5) will be used. Information about all adverse events, whether volunteered by the subject, discovered by Investigator questioning, or detected through physical examination, laboratory testing, or other means, will be collected, and recorded on the Adverse Event CRF page and followed as appropriate. Adverse event monitoring should be continued until adverse event resolution/stabilization (whichever is later).

Medical conditions/diseases present before the injection of study drug are only considered adverse events if they worsen after receiving any study drug. Clinical events occurring before the administration of study drug but after signing the ICF and providing HIPAA authorization are to be recorded on the Medical History/Current Medical Conditions CRF page. All laboratory values are to be reviewed by the Investigator and abnormal values will be graded according to CTCAE Version 4.03 and reported in the study report.

A laboratory abnormality is considered an adverse event if it results in:

- discontinuation from study drug,
- necessitates therapeutic medical intervention,
- if the Investigator assesses the abnormality as an adverse event, or
- any laboratory test that is clinically significant or meets the definition of a SAE

It is expected that wherever possible, the clinical, rather than the laboratory term would be used by the reporting investigator (e.g., anemia versus low hemoglobin value). These adverse events will be recorded on the Adverse Events CRF page and will include all signs, symptoms, or diagnosis associated with them.

As far as possible, each adverse event will also be described by:

1. Description
2. Duration (start and end dates)
3. CTCAE Grade 1 through 5 or severity if CTCAE is not available
4. Relationship to the study drug - related or not related
5. Relationship to the dosing procedure – related or not related
6. Action(s) taken with study drug

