7.3. Multi-Center Studies

This is a multi-center study. Given the small sample size of the study, no site effect will be considered in any statistical analysis.

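### Programmed laboratory grades use generic AMA ranges although samples are run at local laboratories, so results between the AMA-based and local cut-points will be misgraded

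*SAP*

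**What the plan says.** SAP 10.2 (Clinical Laboratory Evaluations) sets the rule: "Severity grades will be programmatically calculated using standard American Medical Association" (AMA) normal ranges, applied with the quantitative CTCAE 4.03 criteria. Protocol 14.3.5 (Clinical Laboratory Tests) contains the same rule, so the SAP has not departed from the protocol.

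The surrounding text describes a different source for the data:

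- Protocol 12.1.3.1 (Cycle 1) has the samples analysed on site: "Clinical laboratory tests (local laboratories". The synopsis lists seven study centers.
- SAP 7.3 confirms "This is a multi-center study" and plans no site effect; SAP 7.1 pools all centers.
- Protocol 6.1, criterion 16d, judges entry by "Creatinine within the institution's laboratory upper limit of normal or calculated creatinine clearance". Criteria 16c, 16e and 16f use multiples of the ULN for coagulation, ALT/AST and bilirubin.
- Protocol 13.1 describes a separate review by the site: "All laboratory values are to be reviewed by the Investigator and abnormal values will be graded according to CTCAE Version 4.03". AMA ranges are not mentioned there.

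SAP 10.2 also plans shift tables by low, normal and high category, and high/low flags in the listings. It does not say which limits define them.

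**The concern.** A reference range belongs to an assay and a laboratory. Where a grade is defined relative to the limit of normal, replacing the laboratory's own limit with a generic one moves every cut-point by the ratio of the two limits. The ratio can differ between centers, and pooling without a site term carries the shift into the treatment summaries.

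Protocol 9.2 names increases in GGT, AST, ALT, lipase and creatinine among the potential effects of INT230-6. These are the kinds of test for which the choice of limit is likely to matter.

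As written, the same result can be judged against the institution's limit at entry and against a generic limit in the analysis. The site's own CTCAE grade and the programmed grade for one value can also disagree. During treatment the protocol has sites act on Grade 3 or higher laboratory abnormalities (8.12, 12.1.3), and neither document says how a conflicting programmed grade would be reconciled or explained.

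**Working it through.** The plan states no misgrading figure to reproduce, so the check asks which results change grade and by how much.

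**Inputs from the documents.** AMA ranges for programmed grades (SAP 10.2, protocol 14.3.5); local analysis (protocol 12.1.3.1); institutional limits for entry (protocol 6.1).

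**Assumptions, because the documents do not give them.** The AMA limits, the local limits, and the CTCAE cut-points. For illustration the cut-points for Grades 1 to 4 are k = 1, 3, 5 and 20 times the ULN.

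**Formula.** Let r = ULN(AMA) / ULN(local), and let x be the result in multiples of the local ULN. The local grade counts the cut-points with x > k. The AMA grade counts those with x / r > k, that is x > k·r. The two grades differ only if x lies between k·min(1, r) and k·max(1, r) for some k.

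**Bands in which the grade changes, in multiples of the local ULN.**

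- r = 0.8 (local limit 1/0.8 = 1.25 times the AMA limit): 0.8 to 1, 2.4 to 3, 4 to 5, 16 to 20.
- r = 1.25 (local limit 1/1.25 = 0.8 of the AMA limit): 1 to 1.25, 3 to 3.75, 5 to 6.25, 20 to 25.

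**Single results at r = 0.8.**

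| x (local ULN) | x / 0.8 (AMA ULN) | Local grade | AMA grade |
|---|---|---|---|
| 0.5 | 0.625 | 0 | 0 |
| 0.9 | 1.125 | 0 | 1 |
| 2 | 2.5 | 1 | 1 |
| 4.5 | 5.625 | 2 | 3 |
| 6 | 7.5 | 3 | 3 |

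The error also runs the other way. At r = 1.25 a result of 6 times the local ULN becomes 6 / 1.25 = 4.8 times the AMA ULN, so Grade 3 becomes Grade 2.

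**Entry compared with analysis.** Criterion 16e admits subjects with hepatic metastases up to 5 times the ULN. If the local limit is 20% to 40% above the AMA limit (assumed), a subject exactly at that bound is read at 5 × 1.2 = 6.0 to 5 × 1.4 = 7.0 times the AMA ULN at baseline.

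**Share of results affected.** Three lognormal distributions were assumed for x: medians 0.6, 0.8 and 1.2 times the local ULN, with log-SDs 0.6, 0.8 and 0.9 respectively. The ranges below span the three.

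| r | Any grade change | Crosses the Grade 3 cut-point |
|---|---|---|
| 0.9 or 1.1 | 4.3% to 8.9% | 0.01% to 1.5% |
| 0.8 or 1.25 | 8.9% to 19.4% | 0.02% to 3.4% |
| 0.7 or 1.4 | 12.1% to 31.9% | 0.02% to 6.1% |

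At r = 1, which is grading against the laboratory's own limit, both shares are zero. The percentages show scale only; none is a document figure.

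**The case against.** The strongest defence is that a single common reference set, specified in advance and identical in both documents, is a transparent convention for descriptive summaries pooled across centers. Numerical values and changes from baseline are also summarised, and every individual result is listed. A clinically significant abnormality is reported as an adverse event on the site investigator's judgement, whatever the program assigns. SAP 10.2 describes no table of shifts in CTCAE grade. Much of this stands, and it limits the harm.

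Four stronger readings are tempting and are not supported:

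- **Every ULN-based grade is wrong wherever the local limit differs.** Only results between the two cut-points change; most results keep their grade in all the scenarios above.
- **The primary safety result is distorted.** The primary measure is the rate of attributed Grade 3 or higher adverse events (SAP 10), and dose-limiting toxicities are drug-related adverse events (protocol 9.1.1). Both rest on investigator-reported events, which are not described as derived from the programmed grades.
- **Toxicity would be hidden.** The listings and adverse event reporting remain in place.
- **The shift categories and flags use AMA limits.** The source of those limits is unstated.

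Bilirubin appears in the eligibility criteria but not in protocol 9.2, so it should not be counted among the potential effects named there.

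Retrospective collection of ranges could also be burdensome: the first subject enrolled in May 2017, the SAP reports final enrollment of 110, and neither document says local ranges were captured. This affects the cost of the change. It does not make a generic limit correct for a local assay.

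**Conclusion.** The point holds within limits. The stated rule will misgrade, by site, results that lie between the AMA-based and local cut-points for tests graded relative to the limit of normal. The harm is to the programmed laboratory grades and, if they use the same ranges, to the low/normal/high shift tables and the listing flags. Nothing in the documents shows an effect on the primary Grade 3 or higher adverse event rate or on dose-limiting toxicities.

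The size is unknown. At an assumed mismatch of 20 to 25%, roughly 9 to 19% of grades change and at most about 3.4% of results cross the Grade 3 cut-point. This rests on assumed ranges, cut-points and distributions. Which tests CTCAE 4.03 grades relative to the limit of normal is also not printed in the documents. This is a cheap improvement to the laboratory safety outputs, not a threat to the trial's main conclusion.

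**What to change.** In SAP 10.2 and protocol 14.3.5, calculate CTCAE grades, low/normal/high shift categories and listing flags from the testing laboratory's own reference range where it is available. Use AMA ranges only where the local range is missing, and footnote those results. State explicitly that the same limits define grades, categories and flags.

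The cost is a wording change plus data-management work to merge site ranges. Sites already need their own limits to apply the eligibility criteria, but some ranges may not be in the database; the AMA fallback covers those without holding up the analysis. No dose, stopping rule or other clinical rule changes.
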